6.12.3. Clinical Laboratory Evaluation

Table [JBAS.6.6](#) describes the clinical laboratory tests to be performed and whether the test will be performed locally or centrally:

Table JBAS.6.6. Clinical Laboratory Tests

Hematology^a	Clinical chemistry^b
Hemoglobin	Serum concentrations of:
Erythrocyte count (RBC)	Total bilirubin
Leukocytes (WBC)	Direct bilirubin
Neutrophils, segmented + bands	Total protein
Lymphocytes	Alkaline phosphatase
Monocytes	LDH
Eosinophils	Creatine kinase
Basophils	Alanine aminotransaminase/serum glutamic pyruvic transaminase
Platelets	Aspartate aminotransferase/ Serum glutamic oxaloacetic transaminase
	Blood urea nitrogen
Immunophenotype^b	Creatinine
Urinalysis^a	Uric acid
Specific gravity	Calcium
pH	Glucose, random (nonfasting)
Protein	Albumin
Glucose	Cholesterol
Ketones	Phosphorus
Blood	Sodium
Leukocyte esterase	Potassium
	Magnesium
ECG chemistry^b	Serum markers^b
Lipase	AFP
Thyroid stimulating hormone	AFP L3
Tri-iodothyronine	PIVKA II
Thyroxine	E-cadherin
Calcium ^c	
Glucose, random (nonfasting) ^c	TGF-β+PF4^b
Albumin ^c	Coagulation^b
Phosphorus ^c	aPPT
Sodium ^c	PT
Potassium ^c	INR
Magnesium ^c	
Special chemistry^b	Fibrotest^b
Cystatin C	Urine C-terminal telopeptides of Type 1 Collagen^b
Troponin I	
BNP	MAP^b
High-sensitivity C-reactive protein	Serum pregnancy test (females only)^a
Hepatitis B and C serology and panels^b	
Hepatitis B surface antigen	
Hepatitis B surface antibody	
Total hepatitis B core antibody	
Hepatitis B e antigen	
Hepatitis B e antibody	
Hepatitis B virus DNA	
Hepatitis C RNA	

Clinical Laboratory Tests (Abbreviations)

Abbreviations: AFP = alpha-fetoprotein; aPTT = activated partial prothrombin time; BNP = brain natriuretic peptide; ECG = electrocardiogram; INR = international normalized ratio; LDH = lactate dehydrogenase; MAP = multi-analyte panel; PF4 = platelet factor 4; PIVKA II = prothrombin induced by vitamin K absence; PT = prothrombin time; RBC = red blood cell; TGF- β = transforming growth factor beta; WBC = white blood cell.

- a Performed at local laboratory.
- b Performed at central laboratory. Performed at a local laboratory if performed during the treatment extension period.
- c Test not performed if both chemistry and ECG chemistry are required.

A listing of all hematology, chemistry (serum, special, ECG), urinalysis, Hepatitis B and C serology and panels, immunophenotype, serum markers, TGF- β +PF4, coagulation (aPTT/PT/INR), fibrotest, urine C-terminal telopeptides of Type 1 collagen, and multi-analyte panel (MAP) will be provided by treatment, patient, cycle and cycle day. Results will be presented using SI units (International System of Units), when available. Normal reference ranges and flags for out-of-range results will also be included. Relevant hematology and chemistry will be graded according to CTCAE v4.0 grading.

6.12.4. Deaths

Reasons for death will be summarized for all deaths, deaths occurring while on therapy, deaths occurring within 30 days of last dose of study drug, and for deaths on-therapy and within 30 days of last dose of study drug combined. Information regarding death will also be included in a data listing.

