**Figure JBAS.8.2. JBAS extension period design.**

## 8.2. Discussion of Design and Control

Approximately 150 patients will be entered in order to randomly assign 120 patients to 1 of 3 treatment arms using a 1:2:1 allocation ratio in favor of the LY2157299 plus sorafenib arm. A randomized, controlled design is being used in this study. Randomization minimizes systematic

bias in the selection and assignment of patients to study therapy and provides justification for inferential statistical methods to be used on data from this study. The study will use a dynamic allocation method, introduced by Pocock and Simon (1975) (and extended for unequal treatment group sizes by Han et al. [2009]) to minimize imbalance between treatment arms according to factors such as AFP and portal vein thrombosis. Using an appropriate concurrent control arm (which is sorafenib in combination with placebo) enables direct statistical estimation of benefits and harms due to study therapy and minimizes bias in the assessment and interpretation of observed treatment effects. The rationale behind favoring the combination arm in the randomization is that this is the primary treatment of interest to compare with sorafenib alone. However, based on the longer time to progression observed in Study JBAK patients in whom LY2157299 was administered as a monotherapy in a first-line setting, there is medical need of getting more information for efficacy and safety of LY2157299 monotherapy. Therefore, a monotherapy arm is also included and will inform future Phase 3 development. The purpose of the monotherapy arm is to provide a comparison to assess the safety of LY2157299 compared to sorafenib. This is especially important because LY2157299 has shown preclinical cardiac toxicity, which, thus far, has not confirmed in clinical studies. However, sorafenib has known cardiac toxicity in patients. The 3-arm study will provide a better differentiation between the various safety profiles and inform the design of Phase 3. Since OS is not affected by pseudoprogression evaluations, OS is a preferred primary endpoint over TTP or PFS. A Bayesian design can be used to leverage survival data for sorafenib alone from historical clinical trials to benefit from the 2:1 randomization of the combination arm relative to sorafenib alone with the goal of increasing power over an otherwise similar design.

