## 10. Efficacy, Health Outcome/Quality of Life Measures, Safety Evaluations, Sample Collection and Testing, and Appropriateness of Measurements

Terms used to describe the periods during the study are defined below:

- **Baseline (Visit 0):** From the time of screening to the first study treatment (or discontinuation, if no treatment is given)
- **Treatment Start:** First day of study treatment
- **Treatment Period:** Time from treatment start to discontinuation from study treatment
  - During the study period, cycle number will correspond to visit number (eg, Cycle 1 = Visit 1).
  - During the extension period, cycle number will correspond to extension visit number (eg, Cycle 1 = Visit 501).
- **Discontinuation from Study Treatment:** The day the patient discontinues study treatment (summary visit)
  - applies to patients in extension period, too
- **30-Day Safety Follow-Up Period (Visit 801):** The time after the patient discontinues study treatment during which follow-up data are collected. Visit 801 starts 1 day after discontinuation from study treatment and lasts 30 days ( $\pm 3$  days).
  - applies to patients in extension period, too. However, for patients in the extension period, the end of the 30-day safety follow-up period is also the end of their study participation (unless further follow-up is required for cardiac toxicities).
- **Long-Term Follow-Up Period (Visits 802, 803, etc):** Visit 802 starts 1 day after the 30-day Safety Follow-up (Visit 801) and lasts 60 days ( $\pm 7$  days). All subsequent long-term follow-up visits will occur at 60-day intervals ( $\pm 7$  days) (for example, Visit 803, Visit 804, etc.) for as long as the patient remains alive or until the required number of deaths have been observed.
  - not required for patients in extension period unless there are cardiac toxicities

Written informed consent must be obtained prior to any study-specific pretreatment evaluations.

Study procedures related to efficacy, safety, health outcome/quality of life measures, sample collection and testing assessments and their timing are described in the sections below and are shown in the Study Schedule ([Attachment 1](#)).

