### **12.2.11. Safety Analyses**

All safety summaries and analyses will be based upon the Safety Population as defined in Section [12.2.1](#).

Overall exposure to study drug, the numbers of patients completing each cycle, and the dose intensity will be summarized using descriptive statistics. The number of patients with any dose adjustment will be presented for entire treatment period as well as for each cycle. The number of patients with dose reductions, dose delays, or dose omissions will also be summarized, as will the reasons for dose adjustments.

An overall summary of AEs will be provided for AEs deemed by the investigator to be possibly related to study medication and will be repeated for events regardless of study drug causality. Incidence rates of these events will be compared between treatment arms using Fisher's exact test.

Safety analyses will include, but are not limited to, the following:

- all reported AEs, including seriousness, severity, and possible relationship to study drug, using CTCAE terminology and grades
- TEAEs, including seriousness, severity, and possible relationship to study drug, using CTCAE terminology and grades
- dose adjustments for any study therapy
- physical examination and other safety observations, including those specifically targeting the monitoring of cardiac safety
- laboratory measures

AE terms and severity grades will be assigned by the investigator using CTCAE version 4.0. MedDRA version 16 (or higher) will be used when reporting AEs by MedDRA terms. The MedDRA lower level term will be used in the treatment-emergent computation. A TEAE, defined as an event that first occurred or worsened in severity after baseline, will be summarized by SOC and by decreasing frequency of preferred term within SOC.

Laboratory and nonlaboratory CTCAEs will be summarized by CTCAE term and maximum CTCAE grade, including the total for maximum Grades 3 and 4. These summaries will be provided for events regardless of study drug causality and will be repeated for events deemed by the investigator to be possibly related to study medication.

Reasons for death will be summarized separately for on-therapy and within 30 days of last dose of study drug. SAEs will be summarized by preferred term.

Hospitalizations and transfusions during the study treatment period or during the 30-day safety follow-up period will be summarized by treatment group.

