Screen failures	Patients who have signed informed consent, do not meet eligibility criteria and are not treated/randomized.
Randomized	Patients who have been assigned to study treatment but may have not received any study treatment (LY2157299, LY2157299-matched placebo, or sorafenib).
Patients on therapy	Patients who have been randomized to study treatment and have received at least 1 dose of study treatment (LY2157299, LY2157299-matched placebo, or sorafenib).
Study day	If assessment is on or after date of first treatment dose then (date of assessment) – (date of first study treatment dose) + 1 If assessment precedes first treatment dose then (date of assessment) – (date of first study treatment dose) There is no study day 0. Study day 1 is the date of first dose and study day -1 is the day before the first dose.
Cycle day	If assessment is on or after date of first treatment dose then (date of assessment) – (date of first study treatment dose in cycle) + 1 If assessment precedes first treatment dose then (date of assessment) – (date of first study treatment dose in cycle) There is no cycle day 0. Cycle day 1 is the date of first dose in the cycle and cycle day -1 is the day before the first dose.
Baseline	For change from baseline analysis, baseline value is defined as the last reported measure on or before the first dose date (or discontinuation, if no treatment is given). For change from baseline within a cycle, the measure prior to the first dose if that cycle is baseline.
Study treatment period	Time from treatment start to discontinuation from study treatment
Post-discontinuation – short-term follow-up	The short term follow-up period begins 1 day after discontinuation of study treatment and lasts approximately 30 days (Visit 801).
Post-discontinuation – long-term follow-up	The long-term follow-up period begins 1 day after the short-term follow-up period (Visit 801) is completed and continues until death to collect survival data.

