6.12. Safety Analyses

6.12.1. Treatment Compliance and Dose Intensity

The assigned dose of LY2157299 (or matched placebo) for every patient is 300 mg/day and the assigned dose for sorafenib is 800 mg/day for all patients in the combination arms. A prescribed dose is the dose the patient is prescribed to take in each cycle, including adjustments due to dose reductions or omissions within a cycle if prescribed by the investigator.

Treatment compliance is defined by the patient taking the study drug in mg as prescribed.

Dose intensity is expressed as a percentage of actual daily dose (mg) divided by assigned daily dose (mg) across all cycles, including the last cycle that may have been less than 28 days.

Treatment compliance and intensity information for LY2157299 (or placebo) will use collected pill counts of each tablet strength (150 mg and/or 80 mg if dose is reduced) at each cycle and the date of first dose and date of last dose in every cycle and study treatment discontinuation date. The pill counts will determine the extent of patient exposure to study drug. Similarly, treatment compliance and intensity information for sorafenib will use collected pill counts (tablet strength of 200 mg).

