A treatment emergent AE (TEAE) is any AE initially occurring after 1st dose; or if initially occurring pre-dose and ongoing at time of first dose (may be a pre-existing condition or AE) and severity of the reoccurrence is greater than the max severity pre-dose; then the reoccurrence is a TEAE. The time frame post-dose includes end of short term follow up period. The CTC LLT will be used to compare pre-dose and post-dose events in the TEAE algorithm.

1. Compare the post-dose LLT with LLT of preexisting conditions/AEs ongoing at first dose:
 - a. If the post-dose LLT is not present as a pre-dose term, then the AE is a TEAE
 - b. If the LLT is present as a pre-dose term AND the severity increases post-dose compared with the most severe pre-dose grade for the same LLT, then the event is a TEAE
2. Time frame post-dose includes end of short term follow up period – that is, 30 days post discontinuation of study treatment.

Treatment-emergent AEs excludes any AE which maps to a LLT recorded at baseline and has the same or lower severity as that at baseline, even if considered drug related or serious.

Treatment-related AEs are events considered as having at least a suspected relationship to the study drug as entered on the CRF.

If the severity grade or relationship to the study drug of an AE is missing, a worst-case scenario will be assumed (that is, Grade 4 or related for post-dose AEs, and Grade 1 or not related for pre-dose AEs).

Specifically, the following summary tables will be provided:

- An overview of AEs including the number and percentage of patients with ≥ 1 TEAE, ≥ 1 CTCAE Grade 3/4, ≥ 1 SAE, who discontinued study treatment due to AE, discontinued study treatment due to SAE, died due to AE on study treatment, and died due to AE within 30 days of discontinuation from study treatment. Additionally, the number of AEs related to study treatment in each of the previous categories will be given.
- The number and percentage of patients experiencing the following TEAEs by treatment group, SOC and PT:
 - TEAEs
 - Related and regardless of relatedness to study drug
 - TEAEs leading to discontinuation from study treatment
 - TEAEs leading to discontinuation from study treatment by serious criteria
 - Related and regardless of relatedness to study drug
 - SAEs
 - TEAEs by maximum reported CTCAE grade
 - Related and regardless of relatedness to study drug
 - TEAEs grouped by maximum CTCAE grade (Any grade, Grades 1/2, Grades 3/4/5, Grade 5)

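### The SAP's death tables count 30 days from last dose while its other safety windows count from discontinuation, which can shorten the Arm 1 window because LY2157299 is given intermittently

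*SAP*

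**What the plan says.** Two different starting points are used for a 30-day period after treatment.

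- **Last dose.** SAP 6.12.4 summarizes reasons for death in four groups: all deaths, deaths on therapy, "deaths occurring within 30 days of last dose of study drug", and the second and third combined. It also lists deaths. Protocol 12.2.11 has the same starting point: "Reasons for death will be summarized separately for on-therapy and within 30 days of last dose of study drug".
- **Discontinuation.** SAP Table JBAS.6.1 defines the study treatment period as "Time from treatment start to discontinuation from study treatment", and continues: "The short term follow-up period begins 1 day after discontinuation of study treatment and lasts approximately 30 days". SAP 6.12.2 closes the treatment-emergent window 30 days after discontinuation. Its overview table has a row for patients who "died due to AE within 30 days of discontinuation from study treatment". SAP 6.12.5 collects hospitalizations and transfusions over the same post-discontinuation period.

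The two dates are separate data items. SAP 6.12.1 uses the "date of last dose in every cycle and study treatment discontinuation date".

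The dosing schedules differ by arm (SAP 6.12.1.1). LY2157299, the only drug in Arm 1, is taken for 14 days and then paused for 14. Sorafenib, in Arms 2 and 3, is taken throughout the 28-day cycle.

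**The concern.** Because Arm 1 has a planned two-week pause in every cycle, a patient in that arm can be well past the last dose on the day of discontinuation. A patient taking sorafenib daily is not. A window that starts at last dose then reaches less far beyond discontinuation in Arm 1. Two arms with the same mortality and the same stopping days would have different time at risk in the 30-day row and the combined row, with the difference favoring monotherapy.

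The SAP also becomes inconsistent with itself. The same AE death can be counted in the overview's 30-day row and left out of the 30-day death rows. At stake is a descriptive safety comparison that bears on what Arm 1 is for. Protocol 8.2 says: "The purpose of the monotherapy arm is to provide a comparison to assess the safety of LY2157299 compared to sorafenib".

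**Working it through.** **Inputs.** The death window is 30 days from last dose (SAP 6.12.4). LY2157299 is taken for 14 days per cycle, with 10 to 14 permitted, and a cycle is 28 days, with 26 to 31 permitted (SAP 5.1). Sorafenib is taken on all 28 days (SAP 6.12.1.1). The control hazard is 0.0216 per week (SAP 5.2), used here only to show size. Arm 1 has 30 planned patients (SAP 5.2). The plan gives no figure of its own to reproduce on this point.

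**Step 1: the window after discontinuation.** Window = 30 - (discontinuation day - last-dose day).

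| Stop at cycle end | Last dose | Gap (days) | Days left in window |
|---|---|---|---|
| Uninterrupted sorafenib, 28-day cycle | Day 28 | 0 | 30 |
| LY2157299 alone, 28-day cycle | Day 14 | 14 | 16 |
| LY2157299 alone, 26-day cycle | Day 14 | 12 | 18 |
| LY2157299 alone, 31-day cycle | Day 14 | 17 | 13 |
| LY2157299 alone, 28-day cycle | Day 10 | 18 | 12 |
| LY2157299 alone, 31-day cycle | Day 10 | 21 | 9 |

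On the regular schedule the ratio is 16/30 = 0.53. The permitted range is 9 to 18 days. A stop on the next Day 1 (Day 29) leaves 30 - 15 = 15 days.

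**Step 2: the average instead of the extreme.** If the stopping day is uniform over Days 1-28 (assumption), the gap is 0 on Days 1-14 and runs from 1 to 14 on Days 15-28. The mean gap is 105/28 = 3.75 days, so the mean window is 30 - 3.75 = 26.25 days.

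**Step 3: size in deaths.** With a constant hazard (assumption), the proportion dying in d days is 1 - exp(-hazard × d/7). The 2-fold and 3-fold hazards are assumptions for patients who have stopped treatment.

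| Hazard | 16 days | 26.25 days | 30 days | Fewer deaths per 30, average case | Fewer deaths per 30, all stop on Day 28 |
|---|---|---|---|---|---|
| 0.0216 | 4.8% | 7.8% | 8.8% | 0.3 (12%) | 1.2 |
| 2 × 0.0216 | 9.4% | 15.0% | 16.9% | 0.6 (12%) | 2.3 |
| 3 × 0.0216 | 13.8% | 21.6% | 24.2% | 0.8 (11%) | 3.1 |

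**Step 4: the internal conflict, which needs no mortality assumption.** Take an AE death 35 days after last dose in an Arm 1 patient with a 14-day gap. It is 35 - 14 = 21 days after discontinuation. It is inside the overview's 30-day row in SAP 6.12.2 and outside the 30-day row in SAP 6.12.4.

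**The case against.** Last dose is a legitimate starting point. Counted from it, every arm has exactly 30 days, and protocol and SAP agree on it for this table. Protocol 5.1.3 reports a half-life of 6 to 8 hours and full elimination over the 14-day pause, so an exposure-based window is defensible. Starting at discontinuation removes one inequality and creates another: an Arm 1 patient who stops on Day 28 is then followed to 30 + 14 = 44 days after last dose. All of this stands, and it is the reason to keep a last-dose row. It does not explain why two tables in the same SAP should count 30-day deaths from different dates. If *on therapy* ended at last dose, the asymmetry would disappear, but SAP 6.12.4 does not say so and the SAP's treatment period runs to discontinuation.

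Some stronger inferences are tempting and are not supported:

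- **That Arm 1 would show about 45% fewer early deaths.** This requires every patient to stop alive at cycle end. Scans every 6 weeks from Cycle 2 Day 14 fall nominally on study Days 42, 84, 126 and 168. These are alternately the last dosing day and the last day of the pause.
- **That last dose and discontinuation always nearly coincide in Arms 2 and 3.** Table JBAS.9.3 in the protocol allows a sorafenib delay of up to 30 days before treatment is discontinued. Protocol 7.3.1 lets patients who stop sorafenib for toxicity continue LY2157299 or placebo. Gaps can open in those arms too.
- **That deaths are lost.** The all-deaths row and the listing include every death, and OS has no such window.
- **That comparing early deaths is the stated purpose of Arm 1.** Protocol 8.2 speaks of safety generally, with emphasis on cardiac toxicity, and also of efficacy information. No test is specified for the death table.

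**Conclusion.** The point holds as a minor inconsistency in a descriptive safety table. The 30-day and combined death rows start at last dose, the SAP's other post-treatment windows start at discontinuation, and *on therapy* is not bounded in the deaths section. Dosing schedules make the difference depend on arm: about 16 days (9 to 18) against about 30 for a cycle-end stop, compared with uninterrupted sorafenib.

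That contrast is the worst case. The average shortfall in Arm 1 is nearer 12%, or 0.3 to 0.8 deaths per 30 patients. This rests on a uniform stopping day, a constant hazard of 1 to 3 times the control rate, and no gap in the comparator; sorafenib holds or stops would narrow the contrast. The date arithmetic and the conflict between the two SAP tables rest on none of these assumptions. No objective, decision rule or inference is affected.

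**What to change.** In SAP 6.12.4 and protocol 12.2.11:

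1. Define *on therapy* as the study treatment period, ending at discontinuation of study treatment.
2. Tabulate deaths within 30 days after discontinuation in all arms, and build the combined row on the same basis.
3. Keep the last-dose tabulation as a supplementary, exposure-based row.

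The cost is a few lines of wording and a changed date variable; both dates are already used for the dose-intensity calculation. If the protocol is not otherwise being amended, its section 12.2.1 allows a change that is not a principal feature to be described and justified in the clinical study report. The downside is that the window for an Arm 1 patient stopping at cycle end runs to about 44 days after last dose, so slightly more deaths will be counted in Arm 1. The supplementary row lets a reader see that.
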